5.2 Phase 2: Interactive Consensus Workshop and Trial Design (Months 5-9)

Having performed a survey to establish current practice and equipoise in key clinical scenarios of women presenting in preterm labour, we will convene an interactive working of approximately 40 participants with a broad range of experience and expertise. This workshop will include the co-investigator team, multidisciplinary experts, clinicians, women, patient groups, and key stakeholders to determine what kind of trial/trials still need to be done, and what groups of women should be included to address outstanding research questions. The aim is to use Delphi methodology to refine the clinical uncertainties, to inform the design of a clinical trial.

A two-round Delphi consensus methodology will be used to reduce the survey list of clinical uncertainties into a short-list, prioritising those clinical scenarios which are both uncertain and important. The Delphi methodology enables all stakeholders to participate in a consensus process which assesses the extent of agreement (about priorities) and then resolves disagreement (Sinha, Smyth et al. 2011). All stakeholder groups including parents, healthcare professionals, researchers and healthcare regulators will be invited to participate.

Two rounds of the Delphi process will take place using a web-based survey application that has been developed by the University of Liverpool (DelphiManager) and adopted by the Comet Initiative (comet-initiative.org/delphimanager). Our survey will be hosted within an online portal and infrastructure designed by the University of Liverpool. Before entering the exercise, participants will be asked to register, provide demographic details, and commit to all rounds. After this has been reviewed a unique identifier will be allocated. The unique identifier will anonymise participant responses but also provide a means to send completion reminders. Participants will also be given the option of a paper (postal) questionnaire, if they do not have access to a computer.

a) Pilot

The Delphi questionnaire will be piloted to ensure the ease of completion by participants prior to recruitment. The Delphi survey will be piloted on the study committee and the PPI panel. This is to ensure that the outcome terminology is understood by stakeholders before allowing them to decide which outcome is important to them in the Delphi. Since those participating in the pilot are part of the study team, formal consent will not be taken.

b) Round One

Potential participants will receive an e-mail linking to the web-based questionnaire embedded within the study's website. (We will send a postal questionnaire to those who state that they do not have regular access to a computer). Initial questions will include the option to add additional scenarios for use in round two before proceeding to scoring. Even though it is likely these additional proposed scenarios would have been previously dropped from the longlist, this failsafe step will be able to identify any scenarios that may merit reconsideration.

Participants will score each clinical scenario listed using the Likert type scale, using a composite of "importance" and "clinical uncertainty" about the scenario in question. The scores will be summarised graphically using the DelphiManager.

c) Round two

The scenarios will be carried forward to round two. An anonymous summary of the responses will be fed back to participants according to each stakeholder group. Participants will be asked to re-score their preference to reach consensus. Any outcomes not deemed important by the pre-specified scale will be dropped.

d) Final Consensus meeting

An interactive consensus meeting will take place following the completion of the Delphi process to validate the final set of scenarios. The meeting will present scenarios retained and dropped by the Delphi process and discuss any scenarios in Delphi round 2 where "no consensus" was found. Only those stakeholders who completed both rounds of the Delphi study will be invited to participate. It is anticipated that 2-3 key participants from each stakeholder group will participate.

At this interactive meeting we will finalise the shortlist of scenarios that will inform the development of resources for the subsequent qualitative phases of the study. The aim is to use the prioritised scenarios to plan the single most important trial (which may have several subgroups of women [e.g. women in labour and women not in labour], and several stratification variables [e.g. twin and singleton women]). Any scenarios not possible to cover in a single trial will be discussed for future separate exploration.

5.2.2 Trial design

We anticipate that the randomised trial will use an efficient design and the PICO will be:

Participants: women in spontaneous preterm labour or with planned preterm delivery Intervention: caesarean section Comparator: vaginal delivery Outcomes: to be determined.

The surveys of current opinion and practice, and the consensus process described above will identify key clinical uncertainties that could be addressed in a clinical trial. These clinical uncertainties will pinpoint subgroups of participants (such as women with breech presentation, or particular gestational ages, for example). The outcomes for the randomised controlled trial will include those that can best address the identified clinical uncertainties, and so determine which interventions will be clinically effective, safe, affordable, and acceptable to women. It will also include those indicated by COMET for preterm birth (van 't Hooft, Duffy et al. 2016). Our primary outcome (on which the trial will be powered) will be one which is considered important

by clinicians and parents, and is measurable with good reproducibility. A sample size calculation will be performed, and the approximate cost of the trial determined.

5.2.3 Mock up of short trial protocol.

Once the trial design is complete, the clinical team and the triallists in the panel will generate a short trial protocol. The qualitative team (helped by our PPI) will use the protocol to develop a descriptive vignette for use in the focus groups discussions.

5.3 Phase 3: Qualitative Design (Months 10-22)

Next we will perform a qualitative study among clinicians and women to determine if clinicians would be willing to recruit into the proposed trial and whether women would be willing to participate. An iterative, inductive approach will be used for the qualitative research in which data analysis will commence as soon as data collection begins. This will allow issues identified during the early phases of data collection to inform areas explored in later stages and possibly also sampling. The two components of the qualitative research – clinician interviews and focus groups with women – will take place in parallel, allowing them to be mutually informing.

5.3.1 Part 1: Clinician interviews

Recruitment and sampling

Clinicians who indicted at the end of the survey (see 5.1.2) that they would be willing to be contacted to take part in an interview will be sampled in light of: (a) their survey responses (e.g., so we draw upon the perspectives of those in favour of caesarean section and vaginal delivery, respectively); and, (b) so there is representation of the different kinds of clinical staff who would be involved in recruiting into the proposed trial (e.g. obstetricians, neonatologists, midwives, research midwives etc.) from different areas.

Individuals selected for an interview will be contacted by the qualitative researcher appointed to the study who will provide them with a participant information sheet for the interview study and a consent form and answer any questions they might have. Assuming the clinician still wishes to take part, the researcher will then arrange a convenient time to interview them on the phone.

If insufficient clinicians completing the survey give their permission to be contacted to take part in an interview, additional health professional recruitment will be undertaken by clinical co-investigators and collaborators on the study who will send out recruitment packs to obstetricians, neonatologists, midwives, research midwives within their networks, containing a participant information sheet, an opt-in form and a consent form. We may also 'snowball' from health professionals who have taken part in an interview by asking them to pass on recruitment packs to colleagues who they think would interested in taking part in an interview. Individuals receiving these recruitment packs will be asked to complete and return opt-in forms directly to the qualitative research team. Individuals who complete the opt-in form will be contacted by the research fellow who will answer any questions they have and arrange a convenient time to interview them on the phone.

Clinicians will be asked to complete and sign the consent form before their interview takes place; as part of the consent process, clinicians will be also be asked for their permission for their interview to be audio-recorded.

Data collection

Clinicians will be sent a brief summary (a short protocol) of the proposed trial design in advance of their interview and this will form the focus of the discussion in the interview. As well as seeking their views on whether (and why), they would be willing to recruit and randomize women, health professionals will be asked about the training, resourcing and other support they would need to deliver the trial were it to go ahead in the future. Health professional interviews will also explore the potentially distinctive challenges of recruiting minority ethnic women into the trial and what additional resourcing and support they feel they would need to optimize these women's participation.

Clinician interviews will be informed by a topic guide, which will help the discussion stay relevant to the study aims, while allowing flexibility for individuals to raise and discuss issues which they perceive as salient, including those potentially unforeseen at the study outset. The topic guide will be informed by literature reviews, inputs from the coinvestigator team, and revised in light of emerging findings (including, potentially, findings from the concurrent focus group study with women), in keeping with the inductive approach proposed for this study.

It is estimated that around 25 clinicians will need to be interviewed to garner a diversity of perspectives and achieve data saturation (that is, when no new findings emerge in new

CASSAVA Version number 2 15th October 2018 IRAS ID 251310 data collection). However, if saturation is not achieved using this sample size, further interviews may be undertaken.

5.3.2 Part 2: Focus groups with women

Concurrent with the clinician interviews, we will conduct 6-8 focus group with women (5-8 individuals per group) who have had a pre-term birth (with representation of those who have had CS or vaginal delivery) and/or who are potentially at risk of preterm birth. Women will be identified from our PPI group, through advertisement by Tommy's and Bliss, and through advertisement via the International Stillbirth Alliance and the network of charities involved in the recent National Bereavement Care Pathway.

Women attending prematurity clinics at Edinburgh and London hospitals or who are identified from Tommy's databases, will be posted or given recruitment packs, containing a covering letter, a participant information sheet, an opt-in form and a consent form. Women may also be recruited through social media, including in collaboration with Bliss and Tommy's. Women will be asked to send their opt-in form directly to the qualitative research team. Women who opt-in to the study will be then be contacted by a member of the qualitative research team who will answer any questions they have and, assuming they still wish to take part, to arrange a time and location for them to take part in a focus group.

Minority ethnic focus groups

We will conduct three of the planned 6-8 focus groups with minority ethnic women to identify and explore potential barriers to trial participation from their perspective and how they think these might be overcome. We plan to approach the following minority ethnic groups (i) Edinburgh-based Pakistani Muslim women (ii) Edinburgh-based Polish women and (iii) London-based Indian women. While Indian women will be able to speak and understand English to a sufficient level to take part in a focus group undertaken in English only, our previous research experience has taught us that it will be necessary to offer Edinburgh-based Pakistani women a focus group undertaken in a mixture of Urdu, Punjabi, and English and Edinburgh-based Polish women a focus group undertaken in a mixture of English and Polish.

We anticipate that some Polish, Pakistani and Indian women will opt-in to the research via recruitment undertaken in prematurity clinics and through Tommy's and Bliss databases and our other networks (see above). However to get sufficient numbers into each of the three dedicated groups and enable inclusion of what are stereotypically seen as 'hard to reach' individuals, additional community-based recruitment will be undertaken, if required. In line with learning from previous qualitative research undertaken by two of the co-investigators ([name]) and others (McLean and Campbell 2003, Sin 2004, Lawton, Ahmad et al. 2005), we will employ local Polish (Edinburgh-based) and Pakistani (Edinburgh-based) bi-lingual researchers. These individuals will recruit women via local community groups and by using known and trusted community members as the initial 'research brokers'. The bilingual researchers will hand out recruitment packs to women in community groups/settings and/or ask research brokers to distribute recruitment packs. Packs will contain an information sheet, an opt-in form and a consent form in English together with versions translated into Polish or Urdu (the written language used by Pakistani women living in Edinburgh), as appropriate.

Women who opt-in into the study will be contacted by a bi-lingual researcher to discuss the study further and to arrange a time and location for their focus group to take place. Pakistani and Polish women will be informed that their focus group will be co-facilitated by the bilingual researcher and hence that they will not be required to speak English in order to take part.

Before participating in a focus group women will be asked to review and complete a consent form. Each participant and the researcher will sign the form and a copy will be given to each woman to keep.

Anonymity of participants: At the beginning of each group, the researcher(s) will highlight the importance of the participants keeping each other's' comments and thoughts confidential and of not sharing these with anyone outside the group.

Data collection

The researcher(s) will provide women with a description of the proposed trial. This will be followed by an open discussion to explore women's views about the trial, the acceptability of randomization and what they think the main barriers and facilitators to recruitment will be. Women will also be asked about the kinds of information they think women would need in

CASSAVA Version number 2 15th October 2018 IRAS ID 251310 order to make a decision about taking part in the trial. A topic guide will be used to orient discussion during the groups and the discussion group will be audio-recorded.

All focus group discussions will be transcribed. Focus groups (or parts of the discussion) undertaken in non-English languages will be translated into English, Confidentiality agreements will be signed by all individuals (e.g. employees of professional transcription companies) involved in the transcription/translation of focus groups discussions.

Reimbursement

Women will be reimbursed for out of pocket expenses and child care and/or given the opportunity to attend a focus group in a venue where they can bring their babies along to maximise attendance and be sensitive to their potential child care responsibilities. Women will be given a voucher for £30 to thank them for their participation.

6 STUDY POPULATION

6.1 NUMBER OF PARTICIPANTS

We plan to recruit in each phase:

Phase 1: Survey. We hope to survey around 200 clinicians on current opinion and practice and 200 members of the public

Phase 2: Consensus workshops and Delphi process will involve clinicians (including members of the co-investigator team), and other key stakeholders including women and their partners. We aim to ensure that 20-40 participants complete at least two rounds of the Delphi consensus exercise.

Phase 3: **Qualitative** interviews and focus groups: We will conduct interviews with clinicians (n=25) and focus groups with women (n=30-60) (i.e. 6-8 focus groups involving 5-8 women per group).

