10 WITHDRAWAL OF STUDY PARTICIPANTS

Participants are free to withdraw from the study at any point. No attempt will be made to record reason for withdrawal. The participant will have the option of withdrawal from

- Ι. all aspects of the study but continued use of data collected up to that point
- П. all aspects of the study with removal of all previously collected data.

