13 STATISTICS AND DATA ANALYSIS

13.1 SAMPLE SIZE CALCULATION

Our planned sample sizes are as follows:

- Clinician survey, n= 200
- Public survey, n= 200
- Interactive working group, n=40
- Focus groups with women, n=30-60
- Interviews with clinicians, n=25

There are no generally accepted guidelines for the optimal size to achieve a consensus in Delphi studies [44] however it is most important to obtain a sample with a broad range of experience and expertise. Approximately 40 participants will be recruited.

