13.2 PROPOSED ANALYSES

The survey data will be used to determine current practice and public opinion. We will use a Likert scale 1-5 and analyse with appropriate non-parametric and/or parametric tests. Where more than 85% of individuals responding to the surveys agree on an answer to a clinical scenario, we will designate the scenario as having good agreement, and being accepted clinical practice. Where less than 50% agree on an answer, we will assume that there is significant uncertainty. Where 50-70% agree, we will designate the scenario as having moderate uncertainty. Where 70-85% agree, we will designate the scenario as having some uncertainty.

Data analysis for the Consensus. Delphi process will involve graphical summation of the scores indicating the whole groups' and individual participant groups' responses using the Delphi Manager. Participants will be asked to score each scenario using the Grading of Recommendations Assessment Development and Evaluations (GRADE) scale for Delphi processes (accessed online). Participants will be asked for example: 'How important is to include the following scenarios in a randomised trial of mode of delivery (caesarean/vaginal) for a preterm baby?' A pre-specified scale and criteria (Williamson, Altman et al. 2012)will be used for dropping and retaining items in the long-list created from the survey: scenarios with >70% participants scoring 7-9 and <30% scoring 1-3 would be included in subsequent rounds.

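### Delphi consensus may reflect who stayed as well as who changed their mind: the >70% rule has no stated denominator, and no step checks whether leavers scored differently in round one

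*Protocol*

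**What the plan says.** **Panel size and completion.** Protocol section 13.1 states "Approximately 40 participants will be recruited" and gives no calculation, noting that "There are no generally accepted guidelines for the optimal size to achieve a consensus in Delphi studies". Section 6.1 adds "We aim to ensure that 20-40 participants complete at least two rounds of the Delphi consensus exercise".

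**Round one.** In section 5.2, participants score each scenario, and "The scores will be summarised graphically using the DelphiManager".

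**Round two.** Scenarios are carried forward and "An anonymous summary of the responses will be fed back to participants according to each stakeholder group". Participants then re-score, and items that do not meet the pre-specified scale are dropped.

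**Retention rule.** Section 13.2: "scenarios with >70% participants scoring 7-9 and <30% scoring 1-3 would be included in subsequent rounds". It does not say whether the percentages are taken over everyone who entered, everyone who scored in that round, or those who completed both rounds.

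**Final meeting.** Section 5.2, item d: "Only those stakeholders who completed both rounds of the Delphi study will be invited to participate". The meeting is to validate the final set and is shown both retained and dropped scenarios. Discussion is specified for those that ended round two without consensus.

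**Loss.** Section 5.2 asks participants at registration to undertake to complete every round, and uses the unique identifier to send reminders. Section 10 says of withdrawal: "No attempt will be made to record reason for withdrawal". No section describes a comparison of leavers with completers.

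**The concern.** A Delphi exercise works by showing people how others scored and letting them revise. Someone in the minority learns this just before deciding whether to answer round two. If such people leave more often than others, the percentage scoring 7-9 rises among those who remain even when nobody has revised a score. The same happens if one stakeholder group leaves more often and scores differently.

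As written, the protocol gives no means of telling this from real convergence. A scenario lifted over the line by attrition would be labelled retained, so it would not be among those the meeting is told to discuss. The people who could have objected would not be invited. The shortlist then informs the trial design and the materials for the qualitative phase, so a false consensus would be passed on to both.

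**Working it through.** **Inputs.** Recruited: about 40 (section 13.1). Completers aimed for: 20-40 (section 6.1). Rule: >70% scoring 7-9 and <30% scoring 1-3 (section 13.2). The protocol gives no expected loss rate, so every loss pattern below is an assumption.

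**The plan's own figure.** No formula stands behind 40 or 20-40, so there is nothing to reproduce. Read together, the lower limit is 20/40 = 50% completion.

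**The second criterion adds nothing here.** If more than 70% score 7-9, fewer than 30% are left to score 1-3. Only the >70% part binds.

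**Scores needed.** With n people in the denominator, the smallest passing count is k(n) = floor(0.7n) + 1.

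| n | k(n) | k(n)/n | k(n)/40 |
|---|---|---|---|
| 40 | 29 | 72.5% | 72.5% |
| 36 | 26 | 72.2% | 65% |
| 30 | 22 | 73.3% | 55% |
| 28 | 20 | 71.4% | 50% |
| 20 | 15 | 75% | 37.5% |

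The last column is the share of the original panel that would suffice if every leaver were a non-supporter. At 20 completers, a scenario that 25 of 40 (62.5%) did not support could pass in that extreme case.

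**Illustration.** Suppose 24 of 40 (60%) score 7-9 in round one, 16 do not, and nobody changes a score. Over all 40 the scenario fails, since 29 are needed.

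- 34 completers: 6 of 16 non-supporters and 0 of 24 supporters leave. 24/34 = 70.6%, passes.
- 30 completers: 8 of 16 and 2 of 24 leave. 22/30 = 73.3%, passes.
- 20 completers: 11 of 16 and 9 of 24 leave. 15/20 = 75%, passes.
- 35 completers: k(35) = 25, more than the 24 supporters. At best 24/35 = 68.6%, fails.

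From this starting point, loss alone cannot carry the scenario over the line while 35 or more remain.

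**Random loss for comparison.** If 20 of 40 leave at random, the number of supporters among the 20 who stay is hypergeometric (40 people, s supporters, 20 drawn). The probability of at least 15 is 0.002 for s = 20 (50%), 0.053 for s = 24 (60%), 0.16 for s = 26 (65%) and 0.37 for s = 28 (exactly 70%). Random loss matters mainly for scenarios already close to the line; the larger concern is differential loss.

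**Would carrying scores forward show it?** Adding the leavers' round-one scores back gives 24/40 in each passing case: 24 + 0, 22 + 2 and 15 + 9 supporters. Each returns to 60% and fails, so each would be flagged.

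**The case against.** Several stronger readings are tempting, and the protocol does not support them.

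- A reader might infer that leavers' round-one scores are never used. They are: section 5.2 summarises round-one scores and feeds them back, and nothing excludes people who later leave. What is missing is any use of those scores to check attrition.
- A reader might infer that only completers count throughout. That is explicit only for the meeting. For the >70% rule the denominator is undefined; that it means those still present is implied by re-scoring, not stated.
- A reader might infer that a 50% loss is declared acceptable. That comes from setting section 6.1 beside section 13.1. The upper end of 20-40 means no loss, and the range could also describe panel size.
- A reader might infer that the meeting cannot correct a false consensus. It sees and validates retained scenarios and could reopen one; it is simply not directed to.
- A reader might infer that the shortlist fixes the trial population. It informs the design, alongside the surveys and the later phases.

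Other counterpoints also have weight. The undertaking at registration and the reminders should reduce loss, and section 13.2 displays responses by participant group, which may make an imbalance visible. Neither shows whether the remaining loss was differential. Section 10 concerns withdrawal, and someone who does not answer round two has not necessarily withdrawn. The loss patterns above are constructed: they need 38% v 0%, 50% v 8%, or 69% v 38% loss among non-supporters and supporters. Dropout is also per person while dissent is per scenario.

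Finally, a leaver-completer table is the kind of detail an analysis plan may hold, and none was available. But the protocol itself sets the rule, calls it pre-specified, restricts the meeting to completers and directs what is discussed there. The gap arises from those stated choices.

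**Conclusion.** The point holds in limited form. The protocol does not define the denominator of its consensus rule, rests final decisions on people still present in round two, and has no step to check whether those who left scored differently. Its stated routing would let an attrition-driven consensus pass without mandated discussion.

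The size cannot be estimated from the document. Under the assumed patterns and unchanged scores, a 15% loss (6 of 40, all non-supporters) is enough to move a 60% scenario above 70%. This shows what the rule permits and is no forecast; it assumes that about 40 people score in round one and that the rule is applied to those who score in round two. The point does not show that dissenters will leave, nor that the planned exercise is invalid. It should be corrected before round one opens, because the check is most credible when specified before any scores are seen.

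**What to change.** Add to Protocol section 13.2, under the Delphi process:

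1. State that the round-two denominator for each scenario is everyone who scored that scenario in round two.
2. Tabulate round-one scores of round-two completers against non-completers, overall and by stakeholder group, with the numbers lost in each group.
3. As a sensitivity check, re-apply the >70%/<30% rule with non-completers' round-one scores carried forward. Limit this to scenarios scored in round one, since those added for round two may have no earlier score, and exclude data removed at a participant's request under section 10.
4. Take any scenario whose status differs between the two applications to the consensus meeting for discussion as not settled, and amend item d of section 5.2 to match.

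**Cost.** One additional table and one re-run of the rule, on data already held under the unique identifiers, with nothing further asked of participants. Carried-forward scores predate the feedback, so they lean against the revision a Delphi is meant to produce. The check should therefore only flag scenarios for discussion and should not replace the main rule. A few scenarios may be reported as less settled than they otherwise would be.
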